8.1 Study endpoints

8.1.1 Primary endpoint

The primary endpoint of this trial is the proportion of patients achieving a mRS score ≤ 2 at 90±14 days after stroke onset. The mRS is the preferred parameter for assessing disability in stroke-related clinical trials. It is an ordinal scale with 7 levels, ranging from 0 to 6, where a score of 6 indicates death (**Appendix 1**). Using the standardized reports, mRS assessments will be conducted by trained and independent investigators and evaluators who are blinded to the assigned groups and the actual treatments received.

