## 2. Evaluation criteria

### 2.1 Efficacy Endpoints

#### 2.1.1 Primary Endpoint

The primary endpoint of this trial is the proportion of patients achieving a mRS score  $\leq 2$  at 90 days after stroke onset. The mRS is the preferred parameter for assessing disability in stroke-related clinical trials. It is an ordinal scale with 7 levels, ranging from 0 to 6, where a score of 6 indicates death.

Assessments will be conducted by trained and independent investigators who are blinded to group assignments and the treatments received. These assessments will be based on standardized follow-up reports completed by blinded study personnel, through either outpatient visits or telephone interviews.

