#### Handling of missing efficacy data

The primary efficacy analysis will be conducted based on the m-ITT population, and every subject must have a 90-day mRS score. If a subject dies before 90 days, they will not be considered missing and will be assigned the highest mRS score of 6 for evaluation. If the 90-day mRS value is missing but the subject's survival is confirmed within 90 days, the last available observation (e.g., from day 5 or discharge) will be carried forward to impute the missing value. For subjects with an unknown survival status at 90 days, the worst possible score (mRS = 6) will be assigned.

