**2) End date of CM:**

- If the year and month are known, the last day of the known month will be used.
- If only the year is known, December 31 of that year will be used.
- If the imputed end date is after the last study visit date, the last study visit date will be used as the end date.

- If the year, month, and day are all missing, no imputation will be performed for the end date.

If the relationship between an AE and the study drug is missing, the AE will be classified as drug-related for the purpose of summary reporting.

For all other missing data in this study, no imputation will be performed, and the data will be analyzed and described in their original state as collected.

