#### 3.9.1 Primary efficacy endpoint

The primary efficacy endpoint, "the proportion of patients with mRS  $\leq 2$  at 90 days after onset," will be statistically described by treatment group. The 95% confidence intervals (CIs) will be calculated using the exact Clopper-Pearson method. Additionally, a bar chart will be used to display the distribution of mRS scores.

When using a superiority hypothesis test, the specific statistical hypotheses are as follows:

Null hypothesis  $H_0: p_T - p_C \leq 0$

Alternative hypothesis  $H_1: p_T - p_C > 0$

$\alpha = 0.025$  (one side)

If the hypothesis is adjusted to a non-inferiority hypothesis after the interim analysis, the specific statistical hypotheses are as follows:

Null hypothesis  $H_0: p_T - p_C \leq -15\%$

Alternative hypothesis  $H_1: p_T - p_C > -15\%$

$\alpha = 0.025$  (one side)

Here,  $p_T$  represent the proportions of patients with mRS  $\leq 2$  in the IVT followed by EVT and EVT alone groups, respectively.

A log-binomial model will be used, assuming the primary endpoint follows a binomial distribution. A log-link function will be applied, with covariates including age, pre-stroke mRS, time from onset to randomization, stroke severity (NIHSS score), and collateral circulation. Adjusted and unadjusted risk difference (RD) and risk ratio (RR) with their 95% confidence intervals will be reported.

For superiority, if the lower bound of the 95% CI of the adjusted RD  $> 0$ , superiority is established.

For non-inferiority, if the lower bound of the 95% CI of the adjusted RD  $> -15\%$ , non-inferiority is established.

Additionally, Chi-square tests (expected cell count  $\geq 5$ ), continuity-corrected chi-square tests (1 expected cell count between 1 and 5), or Fisher's exact test ( $\geq 1$  expected cell count  $< 5$  or any expected cell count  $< 1$ ) will also be used for group comparisons, and P-values will be reported.

The mRS score used in the primary analysis will be based on centralized assessments. If centralized assessments are missing for certain subjects, local investigator assessments will be used by default. Sensitivity analyses will also use local assessments to evaluate the robustness of the results.

A list of all primary efficacy endpoint data for all visits (m-ITT, AT, PPS sets) will be provided.

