### 3.10 Safety analysis

Safety analysis will be performed using the SS dataset.

All adverse events (AEs) reported during the clinical trial will be summarized. AEs will be coded using MedDRA and classified by SOC and PT. For incidence rate calculations, if a subject experiences multiple different AEs, they will be counted as one case for the overall incidence rate. If the same AE occurs multiple times in the same subject, the subject will still be counted as one case for the incidence calculation of that AE. For severity analysis, only the most severe occurrence of the same AE in a subject will be included. Additionally, if a subject experiences multiple AEs within the same SOC and PT, they will only be counted once for the incidence rate calculation within that SOC and PT.

The incidence, number of cases, and rate of all safety endpoints will be summarized. Exact Clopper-Pearson 95% CIs will be calculated for incidence rates. Group comparisons will use chi-square tests, continuity-corrected chi-square tests, or Fisher's exact test, as appropriate, with P-values reported. RD and RR with 95% CIs will also be calculated.

Mortality events will be analyzed using Kaplan-Meier methodology, with median survival time and 95% CIs reported. Kaplan-Meier survival curves will be plotted, and group comparisons will use the log-rank test with P-values reported.

A list of all AEs, serious AEs, adverse reactions, and serious adverse reactions (SS dataset) will be provided.

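### Unknown day-90 survival is scored mRS 6 (death) for efficacy, but the SAP has no rule for it in the mortality analyses, so the two death counts can disagree

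*SAP*

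**What the plan says.** **Meaning of the score.** Protocol 8.1.1 describes the mRS as "ranging from 0 to 6, where a score of 6 indicates death". Appendix 1 of the protocol and SAP 2.1.1 agree.

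**Efficacy rule.** Under the heading on missing efficacy data in SAP 3.2.3: "The primary efficacy analysis will be conducted based on the m-ITT population, and every subject must have a 90-day mRS score". Patients who die before day 90 receive a 6 and are not regarded as missing. For confirmed survivors without a day-90 score, "the last available observation (e.g., from day 5 or discharge) will be carried forward to impute the missing value". Then: "For subjects with an unknown survival status at 90 days, the worst possible score (mRS = 6) will be assigned".

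**Where the score is used.** SAP 3.9.1 says "a bar chart will be used to display the distribution of mRS scores". SAP 3.9.2 analyses the day-90 mRS score, secondary endpoint (3), by ordinal logistic regression. It is the same variable, and no separate missing-data rule is given for it.

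**Mortality.** SAP 2.2 lists all-cause mortality at 7, 30 and 90 days as a safety endpoint. SAP 3.10 reports counts and rates of every safety endpoint with RD and RR, and adds: "Mortality events will be analyzed using Kaplan-Meier methodology, with median survival time and 95% CIs reported". It gives no censoring date and no rule for unknown vital status. SAP 3.2.3 closes with: "For all other missing data in this study, no imputation will be performed".

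**Analysis sets.** The mRS analysis uses the m-ITT set by randomized arm. Mortality uses the safety set, which requires at least one safety follow-up (SAP 3.1.5), by treatment actually received (SAP 3.2.2).

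**The concern.** A patient whose vital status is merely unknown is placed in the category labelled death in one part of the report. In another part the same patient is handled by an unstated rule, which under the no-imputation default would not count a death. Protocol 9.2.2 also requires every death up to day 90±14 to be reported as an SAE. An assigned 6 has no death date and no SAE record, so the SAE listing would disagree with the mRS 6 bar as well.

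Mortality is the first-listed safety endpoint in a trial about giving or omitting thrombolysis. Patients and physicians know the allocation (SAP 1.6), so loss could differ between arms. Any such difference would appear as a difference in deaths in the mRS distribution and the shift analysis, but not in the mortality table. A reader could not tell which was right.

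**Working it through.** **1. The plan's own figure, for the denominator.** SAP 1.5 gives rates of 42.03% and 26.14%, one-sided 0.025 and 80% power. With unpooled variance:

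n per arm = (1.960 + 0.842)² × (0.4203 × 0.5797 + 0.2614 × 0.7386) / (0.4203 − 0.2614)² = 135.76, rounded up to 136.

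136 / (1 − 0.20) = 170 per arm, 340 in total. This matches the plan.

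**2. The count.** Let D be recorded deaths and U the patients with unknown day-90 survival, all in both analysis sets. The mRS 6 count is D + U. If unknowns are not counted as deaths, the mortality count is D. The gap is U: zero if there are none, 17 of 340 at 5%, 34 of 340 at 10%.

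**3. The percentages.** Neither document states an expected mortality or an expected share with unknown survival, so both are assumptions here. Let m be true 90-day mortality and u the share unknown, with loss unrelated to outcome.

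- mRS 6 bar: m(1 − u) + u
- Crude rate, unknowns as non-events: m(1 − u)
- Crude rate excluding unknowns: m(1 − u)/(1 − u) = m
- Kaplan-Meier with unknowns censored: about m

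| m | u | mRS 6 bar | Kaplan-Meier, or crude excluding unknowns | Crude, unknowns as non-events |
|---|---|---|---|---|
| 20% | 5% | 24.0% | 20% | 19.0% |
| 20% | 10% | 28.0% | 20% | 18.0% |
| 30% | 5% | 33.5% | 30% | 28.5% |
| 30% | 10% | 37.0% | 30% | 27.0% |
| 40% | 5% | 43.0% | 40% | 38.0% |
| 40% | 10% | 46.0% | 40% | 36.0% |

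At m = 30% the bar is 3.5 or 7 points above Kaplan-Meier, and 5 or 10 points above the crude rate with unknowns as non-events. Which gap applies depends on the rule that the SAP leaves out.

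**4. Unequal loss, no true difference.** Take m = 30% in both arms, with 5% unknown in one and 10% in the other.

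- mRS 6 bars: 33.5% v 37.0%, a 3.5-point excess in the arm with more loss.
- Crude rate, unknowns as non-events: 28.5% v 27.0%, 1.5 points the other way.
- Kaplan-Meier: about 30% in both.

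At the death cut of the mRS alone, the odds are 0.335/0.665 = 0.504 and 0.370/0.630 = 0.587, an odds ratio of about 0.86 where the truth is 1. The shift model's common odds ratio pools all cut points, so its value needs a full mRS distribution, which the documents do not give.

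**5. Binary endpoints.** For mRS ≤ 2, and likewise for 0–1 and 0–3, a 6 is simply a failure. Relabelling it as a failure with unknown mRS changes no count.

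**The case against.** The strongest reply is that the mRS 6 rule belongs to missing efficacy data. It treats patients who die as not missing and separately gives unknowns the worst score. It can be read as a conservative failure rule, not a statement that the patient died, and reporting observed deaths for safety beside it answers a different question. That is fair for the binary endpoints. It does not hold for a chart and an ordinal model in which 6 means death and the assigned scores cannot be told apart from the recorded ones.

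It is also fair that unknown vital status may be rare. Follow-up may be by telephone, video or in person (SAP 1.8), proxies and healthcare providers may be interviewed (Protocol 8.1.5), and deaths must be reported as SAEs. The SAP nevertheless foresees such patients, since it writes a rule for them. The table shells attached to the SAP were not available and may contain a censoring rule, but an analysis rule should stand in the SAP text.

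A reader might infer more than the documents support:

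- *That the SAP censors these patients.* It does not say so. Censoring is a reasonable inference from the no-imputation rule and usual Kaplan-Meier practice; what can be shown is that the rule is missing.
- *That two different counts are certain.* They require at least one patient with unknown survival.
- *That the counts would otherwise agree exactly.* The m-ITT set by randomized arm and the safety set by actual treatment can differ even with complete follow-up.
- *That up to 68 of 340 patients could be shown as dead without a recorded death.* This treats the whole 20% dropout allowance as unknown survival. Confirmed survivors with a missing score have their last observation carried forward and are not given a 6.
- *That crude mortality must be understated.* It is only if unknowns count as non-events; if they are excluded, it is not under the assumption used here.

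**Conclusion.** The point stands as an unreconciled rule with an effect on the mRS distribution, the shift analysis and the reading of mortality. Followed as written, the plan shows patients without a recorded death in the death category, and gives no rule that would bring the mortality figures into line. Up to three day-90 death figures could appear: the mRS 6 share, the crude rate and the Kaplan-Meier estimate.

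The size cannot be computed from the documents. The illustration of 3.5 to 7 points against Kaplan-Meier rests on 30% mortality, 5% to 10% unknown survival and loss unrelated to outcome; over 20% to 40% mortality the same gap runs from 3 to 8 points. With no unknowns it is zero. The mismatch does not touch the binary primary endpoint, so this is a change that should be made, not a threat to the primary result.

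**What to change.** **SAP 3.2.3, 3.9.1 and 3.9.2.** Keep unknown survival as a failure for the binary mRS endpoints. Reserve mRS 6 for confirmed deaths in the bar chart and the shift analysis, and show unknown survival as a separate category in the chart. In the ordinal model, use multiple imputation of the day-90 mRS for these patients, with the worst-score version as a sensitivity analysis.

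**SAP 3.10.** Censor at the last date known alive. Take the day-7, day-30 and day-90 mortality risks and their RD from the Kaplan-Meier estimate. Add a footnote that reconciles recorded deaths with assigned scores and notes that the m-ITT and safety sets differ in membership and grouping.

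Unknowns are still handled differently by endpoint (failure, imputation, censoring), but each rule is then stated and no assigned score is displayed as a death. If the sponsor prefers not to impute, the minimum is the censoring rule, a separate count of recorded deaths and assigned 6s, and the footnote.

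**Cost.** SAP wording, one imputation step and modest programming. The primary analysis is unchanged.

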## 4. Statistical tables and figures

Statistical tables and figures are included in the "Attachment (TFLs Shell)."

